### **6.1.6 Pregnancy**

Pregnancy in a study subject must be reported to AbbVie within 1 working day of the site becoming aware of the pregnancy. Administration of study drug may be continued at the

investigator's discretion after discussion with the subject, if the benefit of continuing therapy is felt to outweigh the risk (Section 5.4.1). If a subject is discontinued, the subject will be monitored for SVR in the Post-Treatment Period as described in Section 5.4.1.

Information regarding a pregnancy occurrence in a study subject and the outcome of the pregnancy will be collected for pregnancies occurring up to 30 days after the end of treatment.

Pregnancy in a study subject is not considered an adverse event. However, the medical outcome of an elective or spontaneous abortion, stillbirth or congenital anomaly is considered a serious adverse event and must be reported to AbbVie within 24 hours of the site becoming aware of the event.

#### **6.1.7 Toxicity Management**

For the purpose of medical management, all adverse events and laboratory abnormalities that occur during the study must be evaluated by the investigator. All adverse events and laboratory abnormalities will be managed and followed to a satisfactory clinical resolution. Toxicity is deemed "clinically significant" based on the medical judgment of the investigator. The table of clinical toxicity grades "National Cancer Institute Common Terminology Criteria for Adverse Events, Version 4" is to be used in the grading of adverse events and laboratory abnormalities which is available on the Cancer Therapy Evaluation Program (CTEP) website at:

[http://evs.nci.nih.gov/ftp1/CTCAE/CTCAE\\_4.03\\_2010-06-14\\_QuickReference\\_5x7.pdf](http://evs.nci.nih.gov/ftp1/CTCAE/CTCAE_4.03_2010-06-14_QuickReference_5x7.pdf).

Specific toxicity management guidelines apply to the instances of increases in ALT (Section 6.1.7.2).

Where an interruption is required the study drugs should not be interrupted for more than 7 days. If study drugs need to be interrupted for more than 7 days, the Primary Therapeutic Area Medical Director should be contacted and consideration should be given to discontinue the subject.

### **6.1.7.1 Severe Adverse Events**

If a subject experiences a severe adverse event (Grade 3+) or a serious adverse event that the investigator considers to have a reasonable possibility of relationship to study drug, the investigator should assess whether the adverse event can be managed medically without interruption of study drug, or whether study drugs should be interrupted until the event improves. If study drugs are interrupted and restarted and the adverse event recurs, then study drugs should be permanently discontinued.

If a subject experiences a severe adverse event (Grade 3+) or serious adverse event that is considered unrelated (no reasonable possibility) to the study drugs, it is not necessary to interrupt study drugs unless an interruption is required because of the nature of the event (e.g., unable to take oral medications).

The investigator should ensure that all serious adverse events are reported to AbbVie within 24 hours of awareness. Serious adverse event follow-up information, including associated dose interruptions (or discontinuations), must be reported to AbbVie within 24 hours of awareness by entering updated SAE information into the appropriate eCRFs.

Severe adverse events and any associated dose interruptions (or discontinuations) should be entered into the appropriate eCRFs.

### **6.1.7.2 Management of ALT Elevations**

If the ALT increase is confirmed to be  $> 5 \times \text{ULN}$  which is also  $> 2 \times$  baseline value, the recommendations below should be followed:

- Evaluate for alternate etiology of ALT elevation; document in the source, update the medical history and concomitant medications eCRF (if applicable), and obtain additional testing as appropriate.
- Evaluate for a new viral hepatitis infection, including hepatitis A, B and E.
  - If the subject is found to have an active hepatitis B infection, additional evaluation by completion of the eCRF Transaminase Elevations Questionnaire should be performed by the investigator.

- Manage the subject as medically appropriate.
- Repeat ALT, AST, total and fractionated bilirubin, alkaline phosphatase and international normalized ratio (INR) within 1 week. Repeat liver chemistries as indicated until resolution.
- Discontinue study drugs if any of the following is observed at any time:
  - ALT level is  $\geq 20 \times$  ULN in the absence of an alternate etiology.
  - Increasing direct bilirubin or INR or onset of symptoms/signs of hepatitis.
  - At the discretion of the investigator.

Alternate management of ALT increases is permitted with approval of the Primary Therapeutic Area Medical Director.

If the investigator wishes to pursue alternative management of study drugs in the setting of confirmed ALT increases described above, then approval of the Primary Therapeutic Area Medical Director must be obtained.

## **6.2 Product Complaint**

### **6.2.1 Definition**

A Product Complaint is any complaint (see Section 6.0 for the definition) related to the drug component of the product.

For a product this may include, but is not limited to, damaged/broken product or packaging, product appearance whose color/markings do not match the labeling, labeling discrepancies/inadequacies in the labeling/instructions (example: printing illegible), missing components/product, or packaging issues.

Any information available to help in the determination of causality to the events outlined directly above should be captured.

## **6.2.2 Reporting**

Product Complaints concerning the investigational product must be reported to the Sponsor within 24 hours of the study site's knowledge of the event via the Product Complaint form. Product Complaints occurring during the study will be followed-up to a satisfactory conclusion. All follow-up information is to be reported to the Sponsor (or an authorized representative) and documented in source as required by the Sponsor. Product Complaints associated with adverse events will be reported in the study summary. All other complaints will be monitored on an ongoing basis.

Product Complaints may require return of the product with the alleged complaint condition. In instances where a return is requested, every effort should be made by the investigator to return the product within 30 days. If returns cannot be accommodated within 30 days, the site will need to provide justification and an estimated date of return.

The description of the complaint is important for AbbVie in order to enable AbbVie to investigate and determine if any corrective actions are required.

## **8.0 Statistical Methods and Determination of Sample Size**

### **8.1 Statistical and Analytical Plans**

The analysis of pharmacokinetic endpoints will be performed when 12 subjects complete the 2 week intensive PK (IPK) measurements, and these analyses will be done within each age group. For subjects enrolled in Japan, the pharmacokinetic parameters will be summarized separately.

The efficacy, durability of response, resistance, growth and development, patient-reported outcomes, and safety analyses will be performed by age group and overall (across Parts 1 and 2 combined).

The first interim analysis will occur once all subjects participating in IPK in Part 1 complete PT Week 12 or prematurely discontinue from the study. A second interim analysis will occur once all subjects in Part 1 complete PT Week 12 or prematurely discontinue from the study. A third interim analysis will occur once all subjects participating in the IPK portion in Part 2 complete PT Week 12 or prematurely discontinue from the study. A fourth interim analysis will occur once all subjects in

Parts 1 and 2 complete PT Week 12 or prematurely discontinue the study. Final analysis will occur after the completion of the whole study.

SAS® (SAS Institute, Inc., Cary, NC) for the UNIX operating system will be used for all analyses. All statistical tests and all confidence intervals will be two-sided with alpha level of 0.05.

Safety analyses will be performed on all subjects who receive at least one dose of study drug.

Demographic and efficacy analyses will be performed on the intention-to-treat (ITT) population defined as all enrolled subjects who receive at least one dose of study drug, unless otherwise specified.

Sensitivity analyses of the SVR12 endpoint, when applicable, will be performed on the intention-to-treat population modified to exclude subjects who did not achieve SVR12 for reasons other than virologic failure (mITT-VF).

No data will be imputed for any efficacy or safety analysis except for analyses of SVR endpoints (HCV RNA data). HCV RNA values will be selected for the analyses of all SVR endpoints (e.g., SVR4, SVR12, and SVR24) based on defined statistical visit windows. A backward imputation method will be used to impute missing responses for SVR analyses. Detailed statistical methods for all endpoints will be provided in the Statistical Analysis Plan (SAP).

### **8.1.1 Demographics**

Demographics and baseline characteristics will be summarized by age group and overall. As a sensitivity analysis, subjects who receive a dose lower than the final dose chosen for the subject's age group might be summarized separately. The baseline value refers to the last non-missing measurement collected before the first dose of study drug is received in Part 1 or Part 2. Demographics include age, birth year, weight, height, body mass index (BMI), BMI z score (BMI z score will be calculated using WHO published BMI-for-age

z-score tables), weight and height z scores (weight and height z scores will be calculated using WHO published weight-for-age z-score and height-for-age z-score tables), gender, race ethnicity, geographic region and country. Baseline characteristics will include HCV genotype, prior HCV treatment history if applicable, baseline platelets ( $< 90$  or  $\geq 90 \times 10^9/L$ ), baseline albumin ( $< 35$  or  $\geq 35$  g/L), baseline alpha fetoprotein ( $< 20$  or  $\geq 20$  ng/mL), baseline HCV RNA levels (continuous) and ( $< 1,000,000$ ,  $\geq 1,000,000$  to  $< 2,000,000$ ,  $\geq 2,000,000$  IU/mL), baseline fibrosis stage (F0-1, F2, F3, F4), baseline Fibrotest score, baseline APRI, and baseline Child-Pugh score (non-cirrhotic, 5 or 6).

Descriptive statistics will be provided, such as the number of observations (N), mean, and standard deviation (SD) for continuous variables (e.g., age, weight and height z-score) and counts and percentages for discrete variables (e.g., gender and race).

### **8.1.2 Primary, Secondary, and Efficacy Analyses**

The primary and secondary analyses of PK parameters will be performed on subjects in the ITT population with available PK samples, unless otherwise specified.

All efficacy analyses will be performed on the ITT population unless otherwise specified. Subjects who receive a dose lower than the final dose chosen for the subject's age group might be summarized separately. Efficacy analyses will be performed within each age group and overall population.

Plasma HCV RNA levels will be determined for each sample collected by the central laboratory using the Roche COBAS® AmpliPrep/COBAS® TaqMan® HCV Quantitative Test, v2.0. The notation "HCV RNA  $<$  LLOQ" is used to represent all HCV RNA values  $< 15$  IU/mL that are HCV RNA detected or HCV RNA not detected. HCV RNA  $\geq$  LLOQ are all quantifiable values.

#### **8.1.2.1 Primary Endpoints**

The primary endpoint will be steady state AUC of GLE and PIB estimated by non-compartmental pharmacokinetic analysis or population pharmacokinetic analysis,

including AUC at Week 2 in subjects with intensive pharmacokinetics samples and AUC in all subjects with or without intensive PK samples. The 95% confidence interval for the geometric mean of AUC values will be calculated. For subjects enrolled in Japan, the pharmacokinetic parameters will be summarized separately.

### **8.1.2.2 Secondary Endpoints**

The secondary endpoints are:

1.  $C_{max}$  and clearance of GLE and PIB at Week 2;
2. The percentage of subjects with SVR12 by age group and overall;
3. The percentage of subjects with on-treatment virologic failure (i.e., breakthrough, defined as confirmed increase of  $> 1 \log_{10}$  IU/mL above nadir during treatment or confirmed HCV RNA  $\geq 100$  IU/mL after HCV RNA  $< \text{LLOQ}$  during treatment, or HCV RNA  $\geq \text{LLOQ}$  at the end of treatment with at least 6 weeks of treatment) by age group and overall;
4. The percentage of subjects with post-treatment relapse (defined as confirmed HCV RNA  $\geq \text{LLOQ}$  between end of treatment and 12 weeks after the last dose of study drug among subjects who completed treatment as planned with HCV RNA  $< \text{LLOQ}$  at the end of treatment; excluding subjects who have been shown to be re-infected) by age group and overall;
5. The percentage of subjects with new HCV infection (i.e., re-infection) at any time up to the last visit by age group and overall;
6. Assessment of palatability/acceptability of the pediatric formulation by age group and overall.

The number and percentage of subjects achieving SVR12 will be summarized along with a two-sided 95% confidence interval using the normal approximation to the binomial distribution, unless the number of subjects who fail to achieve SVR12 is less than 5, where the Wilson's score method will be used for the confidence interval instead.

In addition, a summary of reason for SVR12 non-response (e.g., on-treatment virologic failure, relapse, reinfection, other) will be provided for each age group.

For the analysis of on-treatment virologic failure, relapse, and re-infection, the number and percentage of subjects will be summarized along with a two-sided 95% confidence interval using Wilson's score method.

For the analysis of post-treatment HCV virologic relapse, completion of treatment is defined as any subject with study drug duration of 52 days, 77 days, and 103 days or greater for subjects allocated to treatment durations of 8 weeks, 12, and 16 weeks, respectively.

For the assessment of palatability/acceptability, the number and percentage of subjects with each categorical answer marked will be presented for each question in the palatability questionnaire at each applicable treatment visit by age group and overall. A listing of palatability questionnaire results and comments for each applicable subject over applicable treatment visits will be produced.

### **8.1.2.3 Additional Efficacy Endpoints**

1. The percentage of subjects with HCV RNA < LLOQ at each post-baseline visit in the Treatment Period (using data as observed);
2. The percentage of subjects with SVR4 by age group and overall;
3. The percentage of subjects with SVR24 by age group and overall;
4. The percentage of subjects who relapsed after achieving SVR12 by age group and overall;
5. Change from baseline to all post-baseline visits in Fibrotest score and APRI by age group and overall.

All rates will be presented with 2-sided 95% confidence intervals using the Wilson's score method.

In addition, a summary of reason for SVR24 non-response (e.g., on-treatment virologic failure, relapse, reinfection, other) will be provided for each age group.

#### **8.1.2.4 Subgroup Analysis**

The number and percentage of subjects with SVR12 will be presented along with the 2-sided 95% confidence interval for the following subgroups if applicable. The subgroup analysis might be restricted to subjects who receive the final dose for the corresponding age group.

- HCV genotype;
- Prior HCV treatment history;
  - For treatment experienced subjects, type of non-response to previous treatment;
- Sex (male or female);
- Baseline fibrosis stage (F0-F1, F2, F3 or F4);
- Baseline HCV RNA level (< 1,000,000, ≥ 1,000,000 to < 2,000,000, ≥ 2,000,000 IU/mL);
- Race (Black versus non-black);
- Ethnicity (Hispanic/Latino versus none);
- Geographic region (North America, Europe, Japan);
- Country (as appropriate);
- Height z-score (< -1, -1 to 1 or > 1);
- BMI z-score (< 25, ≥ 25 to < 30, or ≥ 30 kg/m^2);
- Drug compliance (< 80% versus ≥ 80%);
- In adolescents, former injection drug user (yes, within last 12 months; yes, more than 12 months ago; or no);
- Baseline platelets (< 90, ≥ 90 × 10^9/L);
- Baseline albumin (< 35, ≥ 35 g/L).

The two-sided 95% confidence intervals will be produced using the Wilson's score method if there are at least 10 subjects in the subgroups.

#### **8.1.2.5 Sensitivity Analysis**

As sensitivity analyses, the number and percentage of subjects in the mITT-VF population achieving SVR12, as applicable, will be summarized along with a two-sided 95% confidence interval using the normal approximation and a two-sided 95% confidence interval using the Wilson's score method. The two-sided 95% confidence interval using Wilson's score method will also be calculated as a sensitivity analysis for SVR12 based on ITT population.

#### **8.1.3 Growth and Development**

The following growth and development endpoints will be calculated in the ITT population.

- Growth rate at Post-Treatment Weeks 12, 48, 96 and 144 (defined as change in height over change in age from the previous visit)
- Weight z score
- Height z score
- Body mass index (BMI) z score

Growth rate will be summarized with N, mean and SD together, median and range together at each applicable post baseline visit by gender for all and for age group separately. Weight, height and BMI z scores will be summarized with N, mean and SD together, median and range together at each applicable post baseline visit for all and by age group. Change from baseline in weight and height will be summarized together with other vital signs such as temperature and blood pressure.

#### **8.1.4 Patient Reported Outcomes**

At Baseline, End of Treatment, and Post-Treatment, general quality of life will be assessed using the PedsQL. The PedsQL was designed to measure the core dimensions of

health, as well as role (school) functioning. The PedQL consists of 4 multidimensional scales (Physical Functioning, Emotional Functioning, Social Functioning, and School Functioning) and 3 summary scales (Total Scale Score, Physical Health Summary Score, and Psychosocial Health Summary Score).

Across subjects enrolled in Part 1 and 2 (based on ITT population), summary statistics of change from baseline (n, mean, SD, minimum and maximum) of 3 summary scale scores will be provided by age group and overall. In addition the same summaries will be created separately for subjects who complete all the questionnaires by themselves and for subjects whose parent(s)/guardian(s) always complete the parent/guardian proxy-report.

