### **Patient Reported Outcomes (PRO) Instrument (PedsQL)**

Subjects will complete the PRO instrument, PedsQL, with the assistance of a parent/guardian (where allowed per local regulatory guidelines) on the study days specified in [Appendix C](#). The PRO should be administered as the first procedure at each visit. Subjects will be instructed to follow the instructions provided with the instrument and to provide the best possible response to each item. Site personnel shall not provide interpretation or assistance to subjects other than encouragement to complete the tasks. Site personnel will encourage completion of each instrument at all applicable visits and will ensure that a response is entered for all items.

The PedsQL Generic Core Scales is a 23 item questionnaire designed to measure the core dimension of health as defined by the World Health Organization (WHO), in addition role (school) functioning. The PedsQL consists of 4 Multidimensional Scales (Physical Functioning, Emotional Functioning, Social Functioning, and School Functioning) and 3 Summary Scores (Total Scale Score, Physical Health Summary Score, and Psychosocial Health Summary Score). Completion of the PedsQL should take around 4 minutes to complete. Subjects who are older than 5-years of age and are able to read and understand the questions should complete the questionnaire by themselves. For subjects who are 5-years of age or younger or who are not comfortable with reading the questions, their parent(s)/guardian(s) should complete the parent/guardian proxy-report.

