**Post Treatment Period**

Activity	PT Wk 4	PT Wk 12	PT Wk 24	PT Wk 36	PT Wk 48	PT Wk 96	PT Wk 144	Premature D/C
Vital Signs, Weight, Height, Body Mass Index	X	X	X	X	X	X	X	X
Urine Pregnancy Test a	X							X a
Longitudinal Fibrotest and APRI		X			X	X	X	X
Hematology/Chemistry/Urinalysis b /Coagulation Panel b	X	X			X	X	X	X
HCC Assessment: Liver Ultrasound c			X			X	X	X
HCC Assessment: Alpha fetoprotein c			X		X	X	X	X
Concomitant Medication Assessment d	X	X	X	X	X	X	X	X
Adverse Event Assessment e	X	X	X	X	X	X	X	X
HCV RNA Samples	X	X	X	X	X	X	X	X
HCV Resistance Sample f	X	X	X	X	X	X	X	X
Patient Reported Outcome g		X						X g
HIV RNA Samples h	X	X						
Flow Cytometry h	X							

D/C = Discontinuation

- a. A positive urine pregnancy test requires a confirmatory serum test. (Refer to Section 5.3.1.1 [Pregnancy Test] for additional details.) Females who are experiencing menses or are nearing sexual maturation in the opinion of the PI or who are of childbearing potential should have urine pregnancy testing done through Post-Treatment Week 4. Pregnancy testing will be performed at PT Premature D/C visit only if the subject discontinues prior to PT Wk 4.
- b. Urinalysis will not be conducted after the Post-Treatment Week 4 visit. Urinalysis will be performed at PT Premature D/C visit only if the subject discontinues prior to PT Wk 4. The coagulation panel will be obtained at PTW4 for all patients. For non-cirrhotic subjects: Perform the coagulation panel at visits only if clinically indicated after post treatment Week 4.
- c. HCC assessment for subjects with compensated cirrhosis only.

- d. Concomitant medication will be collected for 30 days after study drug has been stopped, thereafter only antiviral medicines taken for the treatment of HCV and medications taken for SAEs will be recorded. See section 5.2.3.
- e. Non-serious AEs and all SAEs will be collected until 30 days post dosing. Only spontaneously reported SAEs will be collected thereafter. See Section 6.1.
- f. Resistance samples are only collected for patients that meet virologic failure criteria and should be drawn at the confirmatory visit, and if confirmed, at all subsequent visits.
- g. The PRO should be administered as the first study procedure. PRO will be accessed at the Premature D/C visit only if the subject discontinues prior to PT Wk 12.

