Note: The result closest to the scheduled time point will be used. Data must also have Study Drug End Day > 2. Vital signs and growth and development endpoints are collected at every PT visit; hematology, chemistry, urinalysis, and coagulation panels are collected at Post-Treatment Week 4 and PTDC (if subject discontinued prior to Post-Treatment Week 4). For subjects with compensated cirrhosis at baseline, chemistry and coagulation panels are collected to calculate the Child Pugh Score.

Table 6. Visit Windows for Growth Rate Calculation (Post-Treatment Period)

Scheduled Time	Nominal Day (Study Drug End Day)	Time Window (Study Drug End Days Range)
Post-Treatment Week 12	84	3 to 210
Post-Treatment Week 48	336	211 to 504
Post-Treatment Week 96	672	505 to 840
Post-Treatment Week 144	1,008	841 to 1,999
Final Post-Treatment Visit ^a	> 2 days after the last dose of study drug	

a. The last value within the Post-Treatment Period window will be used to define the final post-treatment value. The lower bound of this Final window is Study Drug End Day 3.

Note: The result closest to the scheduled time point will be used. Data must also have Study Drug End Day > 2. For the calculation of growth rate only, height will be assigned to a visit as described in the table above, then growth rate will be calculated as the change in height (millimeter) over the change in age (years) from the previous visit. If height is missing at a visit and/or the previous visit, then growth rate will be missing for the visit.

Table 7. Analysis Time Windows for PRO Instruments (Treatment Period)

Scheduled Visit	Nominal Day (Study Day)	Time Window (Study Day Range)
Day 1/Baseline ^a	1	≤ 1 ^a
Week 8 ^b	56	2 to 70
Week 12 ^c	84	71 to 98
Week 16 ^d	112	99 to 126
Final Treatment Visit ^e	2 to ≤ 2 days after last dose of study drug	

- a. Day of first dose of study drug.
- b. For 8-week treatment only.
- c. For 12-week treatment only.
- d. For 16-week treatment only.
- e. The last value within the window will be used to define the Final Treatment Visit value. The upper bound of this Final window is Study Drug End Day ≤ 2.

Note: Data must also have Study Drug End Day ≤ 2 for all windows. The result closest to the scheduled time point will be used. PRO instruments are collected at Day 1 and End of Treatment Visit, which can be at Weeks 8, 12 or 16 depending on treatment assignment.

Table 8. Analysis Time Windows for PRO Instruments (Post-Treatment Period)

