10.10 Patient Reported Outcomes

The patient reported outcomes data will be analyzed in the ITT population.

At Baseline, End of Treatment, and Post-Treatment Premature Discontinuation, subjects will complete the PRO instrument, PedsQL, with the assistance of a parent/guardian (where allowed per local regulatory guidelines). The PedsQL Generic Core Scales is a 23 item questionnaire designed to measure the core dimension of health as defined by the

World Health Organization (WHO) along with role (school) functioning. The PedsQL consists of 4 Multidimensional Scales (Physical Functioning, Emotional Functioning, Social Functioning, and School Functioning) and 3 Summary Scores (Total Scale Score, Physical Health Summary Score, and Psychosocial Health Summary Score). Subjects who are older than 5-years of age and are able to read and understand the questions should complete the questionnaire by themselves. For subjects who are 5-years of age or younger or who are not comfortable with reading the questions, their parent(s)/guardian(s) should complete the parent/guardian proxy-report.

Across subjects enrolled in Part 1 and 2 (based on ITT population), summary statistics of change from baseline to Week 8 (only applicable to subjects assigned to 8 weeks of treatment), Week 12 (only applicable to subjects assigned to 12 weeks of treatment), Week 16 (only applicable to subjects assigned to 16 weeks of treatment) and Final Treatment Visit and Final PT Visit (n, mean, SD, minimum and maximum) of 3 summary scale scores will be provided by age group and overall. In addition the same summaries will be created separately for subjects who complete all the questionnaires by themselves and for subjects whose parent(s)/guardian(s) always complete the parent/guardian proxy-report.

If a subject starts another treatment for HCV, then all PRO values for this subject measured on or after the start date of the new HCV treatment will be excluded from analyses.

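### The pooled PedsQL change from baseline includes children whose respondent switches from parent to child, and the two rater-specific tables leave those children out at every visit; the effect is small and cheap to remove

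*Protocol*

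**What the plan says.** **Who answers.** Protocol 5.3.1.1 (PedsQL) gives the rule for self-report: "Subjects who are older than 5-years of age and are able to read and understand the questions should complete the questionnaire by themselves". The parent or guardian answers in the other cases: "For subjects who are 5-years of age or younger or who are not comfortable with reading the questions". SAP 10.10 repeats the rule. Neither document ties the respondent to the one used on Day 1.

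**When.** SAP 6.2 states for the Treatment Period: "PRO instruments are collected at Day 1 and End of Treatment Visit, which can be at Weeks 8, 12 or 16". Protocol Appendix C adds Post-Treatment Week 12, with a footnote for early withdrawal: "PRO will be accessed at the Premature D/C visit only if the subject discontinues prior to PT Wk 12". The last planned PedsQL is therefore 12 weeks after the end of treatment.

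**What is summarised.** The ITT population is used, and protocol 8.1.4 plans the main table as follows: "summary statistics of change from baseline (n, mean, SD, minimum and maximum) of 3 summary scale scores will be provided by age group and overall". Two further sets of tables cover "subjects who complete all the questionnaires by themselves and for subjects whose parent(s)/guardian(s) always complete the parent/guardian proxy-report". SAP 10.10 keeps both sets and uses the same condition for the second: "subjects whose parent(s)/guardian(s) always complete the parent/guardian proxy-report".

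**What is not covered.** SAP 6.3 deals with unanswered PedsQL items and with data after a new HCV treatment. The PRO windows in SAP 6.2 deal with timing. Neither mentions a change of respondent.

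**The concern.** Parents and children need not score the same state alike. When the parent answers on Day 1 and the child answers later, the difference between the two scores contains a change of rater as well as any change in quality of life, and the two cannot be separated. The plan's own respondent rule produces such children, because the age limit lies inside the youngest age group or at its upper edge. They enter the pooled table without restriction.

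The rater-specific tables avoid this by requiring the same respondent at every assessment. That condition is set per child rather than per comparison. A child with parent reports on Day 1 and at end of treatment, then a self-report at Post-Treatment Week 12, has a sound Day 1 to end-of-treatment proxy change. The child is still removed from the proxy table, so membership of the end-of-treatment summary depends on something that happens after end of treatment. The removed children are not a random subset: they are those just below the age limit at Day 1, or those gaining reading ability.

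**Working it through.** The documents give no sample size, variance or rater-difference figure for PedsQL, so there is no planned figure to reproduce. The check sizes the age-driven part of the switching.

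**Inputs from the documents**
- Width of the youngest age group: 3 years (3 to < 6).
- Day 1 to end of treatment: 8 or 12 weeks. Day 1 to Post-Treatment Week 12: 20 or 24 weeks.
- Children in the group: about 22 on the final dose (protocol 5.5.3), or 81/3 = 27 if the 81 Part 2 children (protocol 5.1) split equally.

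**Assumptions (not in the documents)**
- Age at Day 1 is uniform over 3 to < 6.
- The gap between self and parent scores is 5 to 10 points, in one direction.
- The SD of change is 10 to 15 points (used for precision only).

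**Share crossing the age limit** = (weeks × 7 / 365.25) / 3. The share is the same whether 5 years or younger ends at the fifth or the sixth birthday.

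| Visit | Weeks from Day 1 | Share | N = 22 | N = 27 |
|---|---|---|---|---|
| End of treatment, 8-week course | 8 | 5.1% | 1.1 | 1.4 |
| End of treatment, 12-week course | 12 | 7.7% | 1.7 | 2.1 |
| Post-Treatment Week 12, 8-week course | 20 | 12.8% | 2.8 | 3.4 |
| Post-Treatment Week 12, 12-week course | 24 | 15.3% | 3.4 | 4.1 |

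That is about 1 to 2 children by end of treatment and 3 to 4 by Post-Treatment Week 12. The chance that at least one child crosses by Post-Treatment Week 12 on an 8-week course is 0.95 (N = 22) to 0.975 (N = 27). All of these are ceilings for age-driven switching, because a child past the limit self-reports only if also able to read and understand the questions.

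**Usable pairs lost from the proxy table.** On either course, the children who cross between end of treatment and Post-Treatment Week 12 are those crossing in 12 weeks: 7.7%, or 1.7 to 2.1 children, again at most.

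**Shift in the pooled mean change at Post-Treatment Week 12** = share × assumed gap.
- Low end: 0.128 × 5 = 0.64 points.
- High end: 0.153 × 10 = 1.53 points.

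**Precision of that mean**, as the 95% half-width 1.96 × SD / √N.
- SD 10, N = 27: 1.96 × 10 / √27 = 3.8 points.
- SD 15, N = 22: 1.96 × 15 / √22 = 6.3 points.

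**Not sized.** Reading ability can also change the respondent in a child already past the age limit, including at older ages such as 6 to < 9. The documents give no rate for this, so it could add to the counts above.

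**The case against.** The strongest reply is that the plan foresaw mixed raters. It provides the same summaries, hence also by age group, for children who always self-report and for those always reported by proxy. A result for ages 3 to < 6 free of rater change is therefore already planned. This stands. A reader might infer that the rater-specific tables cause the mixing by dropping switchers. They do not: the exclusion is what keeps them clean. Only the pooled table mixes raters; the fault of the other two is a small loss of usable pairs.

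The second reply is that the effect is small. This stands too. Crossing the age limit is not enough to change the respondent. PedsQL is not among the primary or secondary endpoints (protocol 5.3.3 and 8.1.2.2), is summarised without a test, and is nowhere named as a leading result. The likely shift is well inside the uncertainty of the mean.

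The third reply is that consistency by visit pair is partly a preference. It lets the set of children differ between visits and takes mixed pairs out of a table specified on the ITT population. That is a fair cost. It can be met by showing the pooled table with and without the mixed pairs.

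What remains is that neither document says who answers after Day 1, the pooled table has no rule for a change of respondent, and a later switch removes an earlier valid change.

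**Conclusion.** The point holds as a minor weakness of a descriptive analysis. For switchers, the pooled change mixes rater with quality of life. The rater-specific tables are sound but discard some valid same-rater changes. In the 3 to < 6 group, age-driven switching reaches at most about 13% to 15% by Post-Treatment Week 12 (3 to 4 children). It moves the pooled mean by at most about 0.6 to 1.5 points, against a half-width of about 4 to 6 points. The counts rest on uniform age and on N = 22 to 27. The shift rests on an assumed gap of 5 to 10 points, and the half-width on assumed SDs. Switching through reading ability is extra and cannot be sized from the documents.

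A reader might apply the 16-week course to the whole group and arrive at 28 weeks, 18% and 4.8 of 27 children, with a shift of up to 1.8 points. The documents do not support that. Protocol Table 5 gives 16 weeks only to treatment-experienced genotype 3 subjects, and Table 6 (Japan) has no 16-week course. The roughly 12 intensive-PK children per age group must be treatment-naïve. The 16-week course therefore cannot describe the group.

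**What to change.** 1. In protocol 8.1.4 and SAP 10.10, define rater consistency by visit pair. A child enters the rater-specific change at a visit when the same respondent type completed Day 1 and that visit.
2. Exclude mixed pairs from the pooled change summary, or show that summary with and without them.
3. Report the number of mixed pairs by age group and visit.
4. In protocol 5.3.1.1, state whether the Day 1 respondent type is kept through Post-Treatment Week 12, and say whether the age limit is the fifth or the sixth birthday.

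**Cost.** This needs wording in two sections of the protocol and one of the SAP. No new data are needed, because the planned split already requires the respondent type at each assessment. A few mixed pairs leave the pooled table, and the children contributing can differ slightly from visit to visit. In return, the pooled change becomes interpretable and up to about two Day 1 to end-of-treatment pairs return to the proxy table for ages 3 to < 6.
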